Appendix C New York Heart Association Classification of Heart Failure

Class	Patient Symptoms
I	No limitation of physical activity. Ordinary physical activity does not cause undue fatigue, palpitation, dyspnea (shortness of breath).
II	Slight limitation of physical activity. Comfortable at rest. Ordinary physical activity results in fatigue, palpitation, dyspnea (shortness of breath).
III	Marked limitation of physical activity. Comfortable at rest. Less than ordinary activity causes fatigue, palpitation, or dyspnea.
IV	Unable to carry on any physical activity without discomfort. Symptoms of heart failure at rest. If any physical activity is undertaken, discomfort increases.

Source: American Heart Association

Appendix D Canadian Cardiovascular Society Angina Grading Scale

Grade	Description	
I	Ordinary physical activity does not cause angina, such as walking and climbing stairs. Angina with strenuous or rapid or prolonged exertion at work or recreation	
II	Slight limitation of ordinary activity. Walking or climbing stairs rapidly, walking uphill, walking or stair climbing after meals, or in cold, or in wind, or under emotional stress, or only during the few hours after awakening. Walking more than two blocks on the level and climbing more than one flight of ordinary stairs at a normal pace and in normal conditions	
III	Marked limitation of ordinary physical activity. Walking one or two blocks on the level and climbing one flight of stairs in normal conditions and at normal pace	
IV	Inability to carry on any physical activity without discomfort, anginal syndrome may be present at rest	

Source: Campeau 1976

Appendix E Predictors Composing the PHASES Aneurysm Rupture Risk Score

PHASES aneurysm risk score	Points	
(P) Population	·	
North American, European (other than Finnish)	0	
Japanese	3	
Finnish	5	
(H) Hypertension	·	
No	0	
Yes	1	
(A) Age	.	
<70 years	0	
≥70 years	1	
(S) Size of aneurysm	·	
<7.0 mm	0	
7.0-9.9 mm	3	
10.0-19.9 mm	6	
≥20 mm	10	
(E) Earlier SAH from another aneurysm	·	
No	0	
Yes	1	
(S) Site of aneurysm	'	
ICA	0	
MCA	2	
ACA/Pcom/posterior	4	

Source: Greving et al. 2014

Abbreviations: ACA=anterior cerebral arteries (including the anterior cerebral artery, anterior communicating artery, and pericallosal artery); ICA=internal carotid artery; MCA=middle cerebral artery; Pcom=posterior communicating artery; posterior=posterior circulation (including the vertebral artery, basilar artery, cerebellar arteries, and posterior cerebral artery); SAH=subarachnoid hemorrhage

Note: To calculate the PHASES risk score for an individual, the number of points associated with each indicator can be added up to obtain the total risk score.

Appendix F Prohibited and Restricted Concomitant Medications

Subjects who must take prohibited medications will not be eligible for the study.

Subjects who require current treatment with a prohibited medication will be discontinued from the study.

Subjects who have previously taken a prohibited medication will be discontinued from the study unless:

- the prohibited medication has been discontinued AND
- discontinuation from the study presents an unacceptable medical risk to the subject

The justification to allow the subject to continue in the study will be made by the Sponsor/Medical Monitor with medical input from the Investigator, and will be documented. If allowed to remain in the study, this will be reported as a major protocol deviation and not a waiver.

The table below lists prohibitions and restrictions by medication class, including representative medications within class. A **prohibited** medication is not allowed. A **restricted** medication is allowed only under certain conditions.

Medication Class	Medicationa	Prohibition/restrictions
Amyloid beta- directed monoclonal antibodies and other anti-tau therapies	PROHIBITED aducanumab lecanemab donanemab	Prohibited from Screening through the end of Visit 6 (EOT/ET) (see also exclusion criterion in Section 4.2)
Antipsychotics	PROHIBITED All in class	 Must be completely discontinued by 3 days prior to Baseline (i.e., no antipsychotic dose during the 3 days prior to the day of the Baseline visit) as determined by the Investigator in discussion with the Medical Monitor Prohibited through the end of Visit 6 (EOT/ET)
Anticholinergics	PROHIBITED • benztropine • biperiden • trihexyphenidyl • oral diphenhydramine	 Centrally acting anticholinergic medications must be discontinued at least 2 weeks or 5 half-lives (whichever is longer) prior to the Baseline visit. Long-term or chronic use is prohibited through the end of Visit 6 (EOT/ET)
	RESTRICTED • benztropine • biperiden • trihexyphenidyl • oral diphenhydramine	Short-term use of centrally acting anticholinergics, including anti-allergy medications, is allowed to treat an adverse event.

Medication Class	Medication ^a	Prohibition/restrictions
	UNRESTRICTEDtrospiumoxybutynintopical diphenhydramine	Peripherally acting anticholinergic medications and topical diphenhydramine are allowed without restriction
Anticonvulsant and mood stabilizers	PROHIBITED carbamazepine lamotrigine lithium phenytoin valproate gabapentin pregabalin	 Must be discontinued 5 half-lives prior to the Baseline visit Prohibited through the end of Visit 6 (EOT/ET) Valproate, gabapentin, and pregabalin prohibited only when prescribed for the treatment of epilepsy
	RESTRICTEDvalproategabapentinpregabalin	Valproate, gabapentin, and pregabalin may be used for the treatment of conditions other than epilepsy if dose unchanged for at least 4 weeks prior to the Baseline visit and expected to remain unchanged until the subject's final visit.
Antidepressants	PROHIBITED mirtazapine nefazodone fluvoxamine mianserin amitriptyline nortriptyline imipramine trimipramine clomipramine esketamine ketamine trazodone	 Must be discontinued at least 2 weeks or 5 half-lives (whichever is longer) prior to the Baseline visit Prohibited through the end of Visit 6 (EOT/ET)
	RESTRICTED citalopram escitalopram venlafaxine desvenlafaxine (Other SSRI medications such as sertraline are allowed and not restricted.)	 If the subject is remaining on these restricted medications, the dose must be unchanged for at least 4 weeks prior to the Baseline visit and expected to remain unchanged until the subject's final visit. Desvenlafaxine is restricted to a maximum dose of 50 mg/day. Citalopram, escitalopram, and venlafaxine can prolong the QT interval and are only allowed under the following conditions: The subject has a Baseline ECG with a QTcF < 425 ms IF QRS duration is <120 ms.

Medication Class	Medicationa	Prohibition/restrictions
		 o The subject has a QTcF <450 ms at Baseline IF QRS duration ≥120 ms. o Citalopram is restricted to a maximum dose of 20 mg/day. Escitalopram is restricted to a maximum dose of 20 mg/day. Venlafaxine is restricted to a maximum dose of 225 mg/day.
Anxiolytics	PROHIBITED chlordiazepoxide diazepam flurazepam RESTRICTED alprazolam clonazepam lorazepam vazepam midazolam triazolam triazolam	 Long-acting benzodiazepines must be discontinued at least 2 weeks or 5 half-lives (whichever is longer) prior to the Baseline visit Prohibited through the end of Visit 6 (EOT/ET) Short- or medium-acting benzodiazepine may be used for acute anxiety. Reasonable efforts should be made to use minimum dose necessary for symptom management. Benzodiazepines (lorazepam up to 1 mg/day or equivalent) are allowed as rescue medication as needed for severe neuropsychiatric or behavioral disturbances. May not be used within 12 hours prior to an assessment visit
Hypnotics and sleeping agents	PROHIBITED zolpidem zopiclone eszopiclone RESTRICTED zaleplon ramelteon	 Must be discontinued at least 2 weeks or 5 half-lives (whichever is longer) prior to the Baseline visit Prohibited through the end of Visit 6 (EOT/ET) May not be used within 12 hours of a cognitive assessment, and efforts should be made to limit agents to lowest dose for the shortest time needed.
Stimulants and wake-promoting agents	PROHIBITED • methylphenidate • modafinil • armodafinil	 Must be discontinued at least 2 weeks or 5 half-lives (whichever is longer) prior to the Baseline visit Prohibited through the end of Visit 6 (EOT/ET) (see Section 4.2 and Section 6.3.6 for procedures related to a positive amphetamine test at study entry)
Non-stimulant ADHD medications	PROHIBITED • atomoxetine • guanfacine	 Must be discontinued at least 2 weeks or 5 half-lives (whichever is longer) prior to the Baseline visit Prohibited through the end of Visit 6 (EOT/ET)
Serotonin antagonists	PROHIBITED • cyproheptadine	 Must be discontinued at least 3 weeks prior to the Baseline visit Prohibited through the end of Visit 6 (EOT/ET)
Antiarrhythmic drugs	PROHIBITED ajmaline amakalant, semantilide amiodarone bretylium	Prohibited from Baseline through the end of Visit 6 (EOT/ET)

Final Version: 2.0

Study: ACP-204-006 Clinical Study Protocol Amendment 3

Medication Class	Medication ^a	Prohibition/restrictions
	 disopyramide dofetilide dronedarone flecainide ibutilide procainamide propafenone quinidine sotalol, d-sotalol 	
Opioids	PROHIBITEDmethadonebuprenorphine	 Must be discontinued at least 2 weeks or 5 half-lives (whichever is longer) prior to the Baseline visit Prohibited through the end of Visit 6 (EOT/ET)
Antimicrobials, antifungals, and antimalarials	PROHIBITED clarithromycin erythromycin levofloxacin moxifloxacin pentamidine roxithromycin	Prohibited from Baseline through the end of Visit 6 (EOT/ET)
	RESTRICTED artenimol/piperaquine azithromycin bedaquiline ciprofloxacin gemifloxacin norfloxacin ofloxacin fluconazole telavancin telithromycin	 Prohibited at Baseline but may be used during the course of the study to treat a bacterial infection (e.g., urinary tract infection, respiratory infection), post-Baseline at the discretion of the Investigator These restricted medications are only allowed under the following conditions: The subject has a Baseline ECG with a QTcF <425 ms IF QRS duration is <120 ms OR The subject has a QTcF <450 ms at Baseline IF QRS duration ≥120 ms.

Abbreviations: ADHD=attention deficit hyperactivity disorder; ECG=electrocardiogram; QRS interval=QRS interval on ECG; QT interval=QT interval on ECG; QTcF=corrected QT interval using Fridericia's correction method

Final Version: 2.0

^a Medications within each class include but are not limited to the examples listed in this table.

Study: ACP-204-006 Final Version: 2.0 Clinical Study Protocol Amendment 3 Date: 15 October 2024

Appendix G Prohibited and Restricted Concomitant Medications: Inhibitors and Inducers of Cytochrome P450 3A4 Enzyme

The information presented here is intended to provide guidance and does not constitute an exhaustive list of strong CYP3A4 inhibitors and inducers. Any questions should be discussed with the Medical Monitor or appropriate designee.

Subjects who require current treatment with a prohibited medication will be discontinued from the study.

Subjects who have previously taken a prohibited medication will be discontinued from the study unless:

- the prohibited medication has been discontinued AND
- discontinuation from the study presents an unacceptable medical risk to the subject

The justification to allow the subject to continue in the study will be made by the Sponsor/Medical Monitor with medical input from the Investigator, and will be documented. If allowed to remain in the study, this will be reported as a major protocol deviation and not a waiver.

Studies in human liver microsomes indicate that CYP3A4 is the major CYP enzyme involved in the oxidative metabolism of ACP-204. Consequently, coadministered potent inhibitors or inducers of CYP3A4 will likely increase or decrease, respectively, the plasma concentrations of ACP-204.

Moderate and strong inhibitors of CYP3A4 are to be stopped at least 7 days or 5 half-lives prior to study drug administration, whichever is longer. Moderate and strong inducers of CYP3A4 are to be stopped 30 days or 5 half-lives prior to study drug administration, whichever is longer.

STRONG	grapefruit juice ^a	MODERATE	grapefruit juice ^a
INHIBITORS	boceprevir (Victrelis®)	INHIBITORS	amprenavir (Agenerase®)
	clarithromycin (Biaxin®)		aprepitant (Emend®)
	cobicistat (part of Stribild®)		atazanavir (Reyataz®)
	indinavir (Crixivan®)		cimetidine (Tagamet®)
	itraconazole (Sporanox®)		ciprofloxacin (Cipro®)
	ketoconazole (Nizoral®)		conivaptan (Vaprisol®)
	lopinavir and ritonavir (Kaletra®)		crizotinib
	mibefradil (Posicor®)		cyclosporine
	nefazodone (Serzone®)		darunavir/ritonavir
	nelfinavir (Viracept®)		(Prezista®/Ritonavir)
	posaconazole (Noxafil®)		diltiazem
	quinupristin (Synercid®)		dronedarone
	ritonavir (Norvir®, part of Viekira		erythromycin (Erythrocin® Lactobionate)
	Pak TM)		2000001011010)

Study: ACP-204-006 Final Version: 2.0 Clinical Study Protocol Amendment 3 Date: 15 October 2024

	- combination treatments including ritonavir, such as: danoprevir and ritonavir elvitegravir and ritonavir indinavir and ritonavir lopinavir and ritonavir paritaprevir and ritonavir and ombitasvir (and/or dasabuvir) saquinavir and ritonavir tipranavir and ritonavir saquinavir (Invirase®) telaprevir (Incivek®) telithromycin (Ketek®) troleandomycin voriconazole (Vfend®)		fluconazole (Diflucan®) fluvoxamine (Luvox®) fosamprenavir (Lexiva®) imatinib (Gleevec®) isavuconazole tofisopam verapamil (Calan®)
STRONG INDUCERS	apalutamide avasimibe carbamazepine (Tegretol®) enzalutamide ivosidenib lumacaftor mitotane phenytoin (Dilantin®) rifampin (Rifadin®, Rifadin IV®, Rimactane®) St. John's Wort	MODERATE INDUCERS	bosentan (Tracleer®) cenobamate dabrafenib efavirenz (Sustiva®) etravirine (Intelence®) lorlatinib modafinil (Provigil®) nafcillin (Unipen®, Nallpen®) pexidartinib phenobarbital (Luminal®, Solfoton®) primidone sotorasib

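### Appendix F allows telithromycin on treatment although Appendix G lists it as a strong CYP3A4 inhibitor, and no visible text reconciles the two appendices

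*Protocol*

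**What the plan says.** **Protocol, Appendix F, antimicrobials.** The prohibited row names "clarithromycin erythromycin levofloxacin moxifloxacin pentamidine roxithromycin" and applies from Baseline through Visit 6. The restricted row names ten drugs, including telithromycin, ciprofloxacin and fluconazole. For these it says "Prohibited at Baseline but may be used during the course of the study to treat a bacterial infection", with urinary and respiratory infection as examples, and "post-Baseline at the discretion of the Investigator". The one further condition is a Baseline QTcF below 425 ms (QRS under 120 ms) or below 450 ms (QRS 120 ms or more). CYP3A4 is not mentioned.

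**Protocol, Appendix G.** Telithromycin is in the strong-inhibitor list; ciprofloxacin and fluconazole are in the moderate list. The stated reason for the lists is that "coadministered potent inhibitors or inducers of CYP3A4 will likely increase or decrease, respectively, the plasma concentrations of ACP-204". The timing rule begins "Moderate and strong inhibitors of CYP3A4 are to be stopped at least" and sets 7 days or 5 half-lives before study drug, whichever is longer. The introduction adds that a subject who needs a prohibited medication is discontinued. It gives an exception route, and a subject kept in by that route is recorded as a major deviation. The title covers both prohibited and restricted drugs, but individual entries are not marked as one or the other.

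**Protocol, body.** Section 1.5.1 says that moderate and strong CYP3A4 inhibitors are prohibited or restricted and points to Appendix G. Section 4.8.2.1 applies both appendices from Screening to the end of Visit 6 and points to Appendix F for QT-prolonging drugs. Section 5.1.3 sets once-daily dosing.

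**The concern.** The protocol restricts CYP3A4 inhibitors because it expects potent ones to raise ACP-204 concentrations. Appendix F nevertheless gives sites an express permission to start one strong inhibitor while ACP-204 is taken daily, and the condition attached to it addresses QT risk only. A drug of the same strength and broadly the same use, clarithromycin, sits in the prohibited row of the same class.

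Two things are at stake. One is subject safety: an interaction that the protocol sets out to avoid is left open for telithromycin. The other is consistent handling. A site working from Appendix F would prescribe and carry on. A site that reads Appendix G as an on-treatment ban would discontinue the subject, or keep the subject under the exception and record a major deviation.

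**Working it through.** No power, alpha or sample-size figure is involved. The check compares the two lists and then works through the possible readings.

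**Step 1: antimicrobials of Appendix F against Appendix G.**

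| Appendix F row | Drugs named | Also in Appendix G | Strength in Appendix G |
|---|---|---|---|
| Prohibited | 6 | 2: clarithromycin, erythromycin | strong, moderate |
| Restricted | 10 | 3: telithromycin, ciprofloxacin, fluconazole | strong, moderate, moderate |
| Total | 6 + 10 = 16 | 2 + 3 = 5 | 2 strong, 3 moderate |

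The other 10 − 3 = 7 restricted drugs (artenimol/piperaquine, azithromycin, bedaquiline, gemifloxacin, norfloxacin, ofloxacin, telavancin) are not named in Appendix G.

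**Step 2: all classes of Appendix F against Appendix G.** Eleven drugs are named in both. Eight are prohibited in Appendix F: carbamazepine, phenytoin, modafinil, nefazodone, fluvoxamine, dronedarone, clarithromycin and erythromycin. The remaining 11 − 8 = 3 are the drugs at issue. Among the strong inhibitors named in both (nefazodone, clarithromycin, telithromycin), telithromycin is the only one allowed on treatment. Nothing visible gives a reason.

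**Step 3: what a site would do under each reading of Appendix G.**

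| Reading of Appendix G on treatment | Clarithromycin | Telithromycin |
|---|---|---|
| Pre-dose washout only | Prohibited by Appendix F | Allowed if the QTcF/QRS limit is met |
| Prohibited | Prohibited by both | Allowed by Appendix F; grounds for discontinuation, or a major deviation if retained, by Appendix G |
| Restricted | Prohibited by Appendix F | Allowed, with no CYP3A4 condition written anywhere visible |

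Clarithromycin has the same status under all three readings. Telithromycin does not. The two moderate drugs follow the telithromycin column. For fluconazole the permission has little practical reach, because the row covers bacterial infection and fluconazole is an antifungal.

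**Step 4: is there a tie-break?** Section 4.8.2.1 names both appendices without ranking them. Section 4.8.2 lets the Investigator treat adverse events and again refers to both. Questions may go to the Medical Monitor, but the restricted row leaves the choice to the Investigator and does not require that contact.

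**The case against.** The strongest reply is that the appendices are cumulative. Section 4.8.2.1 requires both to be followed, Appendix F deals with QT risk and Appendix G with CYP3A4, so meeting the QTcF limit does not waive Appendix G. That is a fair way to read the design, but it does not settle the matter. If Appendix G bans these drugs on treatment, the express permission in Appendix F is empty for them. If it does not, a strong inhibitor is allowed. Appendix G does not say which.

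It can also be said that Appendix G governs on-treatment use. This stands in part: besides the washout it carries a discontinuation rule for prohibited medications. What it lacks is a statement of which listed drugs are prohibited and which are only restricted.

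Other points also limit the concern. The exposure warning is about potent inhibitors, so it bears less on the two moderate drugs. Subjects are to consult the Investigator before taking any medication except in an emergency. Text after the Appendix G table, including the note to its grapefruit-juice entries, is not visible in the copy at hand, so the absence of a precedence rule can be asserted only of the visible text.

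Three stronger readings are tempting, and the documents do not support them.

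- *Subjects will be pushed beyond tested exposure.* The 60 mg arm is already at the top multiple dose given to healthy elderly subjects (60/60 = 1.0), so any rise exceeds it by construction. Healthy adults received multiple doses up to 120 mg, and 120/60 = 2.0. Under the stated dose proportionality, exposure would have to roughly double to reach that level; this is approximate, because exposure is slightly higher in the elderly. The protocol gives no exposure ratio for any inhibitor, and it states a wide preclinical margin and no clinical QTc concern to date.
- *ECG monitoring will miss the harm.* After Week 2 the ECGs are nominally 14 days apart, and at most 14 + 3 + 3 = 20 days with the visit windows. A short course could fall between two of them. That is a limit of monitoring and does not show that harm occurs.
- *Inconsistent discontinuation biases the primary analysis.* The protocol gives no number of users and no rate by arm, so no such effect can be shown.

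**Conclusion.** The inconsistency is real and is clearest for telithromycin: a strong CYP3A4 inhibitor by Appendix G, allowed on treatment by Appendix F on a QT condition alone, while clarithromycin of the same listed strength is prohibited. Ciprofloxacin shares the cross-listing. Fluconazole does too, with little practical effect. Whether those two should be allowed is a clinical decision, and permitting them is not shown to be wrong.

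This is a minor safety and consistency correction. It affects three of the ten restricted antimicrobials, one of them strong. The conclusion rests on the protocol's own classification of the drugs and on the visible text of the two appendices.

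**What to change.** 1. In Appendix F, move telithromycin to the prohibited antimicrobial row, through Visit 6, beside clarithromycin.
2. In Appendix G, state that its moderate and strong inhibitors are prohibited through Visit 6 unless Appendix F expressly excepts them.
3. Name ciprofloxacin and fluconazole either as such an exception or as prohibited, as the clinical team decides.

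The cost is one appendix edit in the next amendment and a memo to sites. Sites lose one anti-infective, at most three. The seven other restricted antimicrobials stay available under the existing QTcF/QRS limits.
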